#### 10.2.4 Handling of Specimens

See section 10.1.4 for handling of specimens. PK specimens will be shipped to Intertek Pharmaceutical Services as outlined (see section 10.2.5).

#### 10.2.6 Methods

All plasma samples will be analyzed for CB-839 by using a validated liquid chromatography tandem mass spectrometry (LC-MS/MS) method of appropriate specificity and sensitivity according to Good Laboratory Practices (GLPs).

### 10.3 Additional Pharmacodynamic Analyses

An evaluation of nucleotide levels as well as a whole exome analysis and an RNA seq analysis will be conducted on baseline and post-treatment tissue biopsies to determine the pharmacodynamic effect of CB-839 and capecitabine on PIK3CA mutant colorectal cancer. This will be conducted during the phase II portion of the trial.

#### 10.3.1 Background and Rationale

Glutamine can be deaminated to generate ammonia as a nitrogen donor for nucleotide synthesis. Since CB-839 blocks glutamine deamination, it should impact nucleotide synthesis. On the other hand, the 5-FU metabolite, FdUMP, inhibits thymidylate synthase and blocks production of dTTP, thereby perturbing levels of other nucleotides through various feedback mechanisms. Taken together, these observations suggest that the combination of CB-839 with 5-FU may have additive or synergistic effects on cellular nucleotide pools. As such, we will determine nucleotide levels in pre- and post-treatment biopsy specimens to determine the impact of CB-839 and capecitabine on nucleotide levels.

Genome wide changes are anticipated to occur with the administration of CB-839 and capecitabine on both the DNA and RNA level. We will therefore use tumor tissue to determine changes occurring in DNA with pre- and post-treatment assessments of the genome via whole genome sequencing and also changes in tumor tissue at the expression level by performing pre- and post-treatment RNA seq analyses.

#### 10.3.2 Collection and Handling of Specimens

See sections 10.1.3 and 10.1.4 for collection and handling of specimens.

### 10.3.4 Methods

Please see the Laboratory Manual for methods on measurement of nucleotide levels, whole exome sequencing and RNA seq.

## **10.4 Generation of Organoids**

### 10.4.1 Background

The purpose of generating organoids from patient tissue specimens is to allow for a sustained source of genetic material upon which additional pharmacodynamic assessments may be performed. This could be either due to limited tissue being available to perform the planned assessments or for material to remain available for future assessments and additional research is conducted.

### 10.4.2 Rationale for Analysis

Given the limited material available for molecular analyses, the generation of organoids from patient tissue specimens is a way to generate additional molecular material that will allow for completion of the planned assessments.

### 10.4.3 Collection of Specimens

During the phase II component of the study, patients will undergo either CT or US guided biopsy of a metastatic focus both prior to the initiation of treatment and 10-15 days following initiation of treatment. The pre-treatment biopsy may be performed up to 14 days prior to the initiation of treatment.

**Tumor Biopsies:** Patients will undergo biopsy in the University Hospitals Cleveland Medical Center (UHCMC) Department of Radiology. If being treated at the Taussig Cancer Institute (TCI) of the Cleveland Clinic, patients will undergo biopsy in the Cleveland Clinic Department of Radiology. If being treated at the Weill Cornell College of Medicine, patients will undergo biopsy in the Weill Cornell College of Medicine Department of Radiology. Use of CT or US guidance for each biopsy will be per the discretion of the physician performing the biopsy and the same metastatic focus of tumor will be biopsied at baseline and 10-15 days following initiation of treatment. If for whatever reason the same lesion cannot be biopsied, a second lesion may be biopsied but this must be noted and recorded. Biopsies will be conducted according to standard practice. Three core biopsies will be obtained for each patient during each biopsy. Fine needle aspiration biopsies are NOT appropriate. Three RNA cryovials will be labeled with the date, patient initials, patients study number and vial number. All study personnel, particularly those handling RNA cryovials, must wear clean gloves. Each of the three core biopsies will be placed in its own cryovial. One cryovial, should contain approximately 1.5 ml of sterile PBS for placement of a fresh specimen and then will be placed on wet ice (see section 10.4 for further details). The remaining two cryovials will immediately be placed in dry ice or liquid nitrogen. Biopsies collected at UHCMC will be transported to the Case Comprehensive Cancer Center, Translational Research and Pharmacology Core Facility for the [name] lab to pick up. Biopsies collected at TCI will be transported to the Cleveland Clinic Central Biorepository for the [name] lab to pick up. Biopsies collected at Weill Cornell College of Medicine will be transported to the laboratory of [name] for processing. The frozen specimens will be processed individually with the second specimen being processed only if insufficient nucleic acid is recovered or if histologic review identifies the presence of necrotic tumor in the first specimen. The remaining fresh frozen specimens will be stored for later use.

#### 10.4.4 Handling of Specimens

##### 10.4.4.1 Handling of Specimens at UHCMC

The vial containing PBS will be placed on wet ice (>5 lb). Personnel from the Case Comprehensive Cancer Center, Translational Research Shared Resource will then be contacted (see below) for transportation, tracking and storage. Upon acquisition, TRSR personnel will contact the [name] Lab to pick up the PBS containing vial for organoid culture and analyses as described in the Laboratory Manual.

10.4.4.2 Handling of Specimens at TCI

The vial containing PBS will be placed on wet ice (>5 lb). Personnel from the Cleveland Clinic Central Biorepository will then be contacted (see below) for transportation, tracking and storage. Upon acquisition, the Cleveland Clinic Central Biorepository personnel will contact the [name] Lab to pick up the PBS containing vial for organoid culture and analyses as described in the Laboratory Manual.

#### 10.4.4.3 Handling of Specimens at Weill Cornell College of Medicine

The vial containing PBS will be placed on wet ice (>5 lb). Personnel from the Laboratory of [name] for processing (see below). The PBS containing vial will be cultured as organoids in the [name] lab. The frozen specimens will be shipped to the [name] laboratory according to procedures described in the Laboratory Manual.

#### 10.4.5 Analytical Laboratory

Fresh specimens at UHCMC and TCI will be processed in the laboratory of [name].

#### 10.4.6 Methods

The generation of organoids will be conducted during the phase II portion of the study. And will require fresh biopsies. These will be obtained as described in section 10.4.3. Patients will undergo a pretreatment biopsy up to 14 days prior to the initiation of treatment, then will undergo a second biopsy on day 10-15 of treatment. Samples will be placed fresh in sterile PBS and placed on wet ice and will be transferred to the laboratory of [name] for processing. Organoids will be generated as outlined in the laboratory manual.

## **11.0 STUDY PARAMETERS AND CALENDAR**

### **11.1 Phase I Study Parameters**

#### **11.1.1 Screening Evaluation**

Screening studies and evaluations will be used to determine the eligibility of each patient for study inclusion. All evaluations must be completed  $\leq$  21 days prior to administration of protocol therapy.

The following should be obtained at baseline:

- Informed consent
- Demographics
- Medical History
- Complete physical examination
- Height
- Weight
- Vital signs including temperature, heart rate, blood pressure and respiratory rate
- Concomitant medications including all over the counter medications and supplements (note that if patients are on a PPI, transition to an H2 blocker prior to treatment is required)
- ECOG performance status
- Baseline symptom/adverse event assessment
- Laboratory studies
  - Complete blood count (CBC) with differential
  - Comprehensive metabolic panel
  - Calculated creatinine clearance if creatinine and/or BUN are abnormal
  - Pregnancy test (if female of reproductive age)
- CT of the chest, abdomen and pelvis
- Baseline CT/US guided tumor biopsy

#### **11.1.2 Treatment Period**

##### **CB-839 and Capecitabine, Cycle 1, Day 1**

All assessments may be performed up to 24 hours prior to treatment.

- Physical examination
- Weight
- Vital signs including temperature, heart rate, blood pressure and respiratory rate
- Concomitant medications including over the counter medications and supplements
- ECOG performance status

- Symptom/adverse event assessment
- Laboratory studies
  - Complete blood count (CBC) with differential
  - Comprehensive metabolic panel
  - Calculated creatinine clearance if creatinine and/or BUN are abnormal
- Administration of CB-839 by mouth twice daily for a 21 day treatment cycle
- Administration of capecitabine by mouth twice daily for first 14 days of 21 day cycle

### **CB-839 and Capecitabine, Cycle 1, Day 8 and Day 15**

Labs may be obtained +/- one day.

- Symptom/adverse event assessment
- Laboratory studies
  - Complete blood count (CBC) with differential
  - Comprehensive metabolic panel
  - Calculated creatinine clearance if creatinine and/or BUN are abnormal
  - Pharmacokinetic assessment prior to morning dose of CB-839 (day 15 only)

### **CB-839 and Capecitabine, Cycle 2 and beyond, Day 1**

All assessments may be performed +/- one day

- Physical examination
- Weight
- Vital signs including temperature, heart rate, blood pressure and respiratory rate
- Concomitant medications including over the counter medications and supplements
- ECOG performance status
- Symptom/adverse event assessment
- Laboratory studies
  - Complete blood count (CBC) with differential
  - Comprehensive metabolic panel
  - Calculated creatinine clearance if creatinine and/or BUN are abnormal
- Administration of CB-839 by mouth twice daily for a 21 day treatment cycle
- Administration of capecitabine by mouth twice daily for first 14 days of 21 day cycle

### **CB-839 and Capecitabine, Cycle 3, sometime between days 15-21 of treatment cycle**

- CT of the chest, abdomen and pelvis for restaging evaluation

**Subsequent CT imaging of the chest, abdomen and pelvis should be performed on an every 9 week basis +/- one week for as long as patient is receiving study treatment.**

## **11.2 Phase II Study Parameters**

### **11.2.1 Screening Evaluation**

Screening studies and evaluations will be used to determine the eligibility of each patient for study inclusion. All evaluations must be completed  $\leq$  21 days prior to administration of protocol therapy (with the exception of the PIK3CA status which may be obtained at any time).

The following should be obtained at baseline:

- Informed consent
- Demographics
- Medical History
- Complete physical examination
- Height
- Weight
- Vital signs including temperature, heart rate, blood pressure and respiratory rate
- Concomitant medications including all over the counter medications and supplements (note that if patients are on a PPI, transition to an H2 blocker prior to treatment is required)
- ECOG performance status
- Baseline symptom/adverse event assessment
- Laboratory studies
  - Complete blood count (CBC) with differential
  - Comprehensive metabolic panel
  - Calculated creatinine clearance if creatinine and/or BUN are abnormal
  - CEA (carcinoembryonic antigen) blood test
  - Pregnancy test (if female of reproductive age)
- CT of the chest, abdomen and pelvis
- Baseline CT/US guided tumor biopsy

#### 11.2.2 Treatment Period

##### **CB-839 and Capecitabine, Cycle 1, Day 1**

All assessments other than tumor biopsy and pharmacokinetics may be performed up to 24 hours prior to treatment.

- Physical examination
- Weight
- Vital signs including temperature, heart rate, blood pressure and respiratory rate
- Concomitant medications including over the counter medications and supplements
- ECOG performance status
- Symptom/adverse event assessment
- Laboratory studies
  - Complete blood count (CBC) with differential
  - Comprehensive metabolic panel
  - Calculated creatinine clearance if creatinine and/or BUN are abnormal
- Administration of CB-839 by mouth twice daily for a 21 day treatment cycle
- Administration of capecitabine by mouth twice daily for first 14 days of 21 day cycle

##### **CB-839 and Capecitabine, Cycle 1, Day 8 and Day 15**

Labs may be obtained +/- one day.

- Symptom/adverse event assessment
- Laboratory studies
  - Complete blood count (CBC) with differential
  - Comprehensive metabolic panel
  - Calculated creatinine clearance if creatinine and/or BUN are abnormal

##### **CB-839 and Capecitabine, Cycle 1, Day 10-15**

- CT/US guided tumor biopsy
- Platelet glutaminase assay (to be obtained the same day as the tumor biopsy)
- Pharmacokinetic assessment prior to morning dose of CB-839 (day 15 only)

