Sample Size	Phase I: 9-24 patients Phase II: 18-40 patients Males and females permitted
Disease sites/ Conditions	Phase I: all solid tumors Phase II: metastatic colorectal cancer, PIK3CA mutant
Interventions	Phase I: Patients will receive CB-839 orally twice daily for 21 days (continuous administration) and capecitabine orally twice daily for 14/21 days. Dosing of CB-839 and capecitabine will occur according to the aforementioned dosing table. Day 15 through CB-839 pharmacokinetics will be assessed. Patients will undergo a disease assessment with CT imaging of the chest, abdomen and pelvis following 3 cycles (9 weeks) of treatment.
	Phase II: Patients will be treated with CB-839 800 mg by mouth twice daily for 21 days (continuous dosing) as well as capecitabine 1000 mg/m  by mouth twice daily for 14/21 days as was determined during the phase I portion of the study. Pre-treatment and post-10-15 day treatment blood samples will be obtained for assessment of glutaminase activity (to be obtained the same day as the post-treatment biopsy). Day 15 blood samples will also be archived for as needed assessment of CB-839 pharmacokinetics. Baseline tissue biopsies and a day 10-15 tissue biopsy will be obtained to assess tissue glutaminase activity and nucleotide levels as well as for whole exome sequencing, RNA seq and for the production of organoids. Patients will be assessed with CT scans of the chest, abdomen and pelvis every 3 cycles (9 weeks). Treatment will continue until disease progression, until unacceptable toxicity develops or per patient/physician preference.

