### 1.2.3 Clinical Pharmacokinetics and Pharmacodynamics

Pharmacokinetic sampling was performed on Cycle 1, Day 1 (C1D1), C1D15 and D1 of each subsequent treatment cycle in each of the conducted phase I studies (17-19). A dose dependent relationship was observed with CB-839 exposure increasing with dose. The half-life of CB-839 was determined to be 4 hours. Additionally, Cmin fell below a target concentration of 200 ng/mL in 46% of patients receiving 400 mg or higher TID regimens while a large majority of patients receiving BID dosing with 600 mg maintained a Cmin greater than the 200 ng/mL target concentration. Additionally, an assessment of the effect of food on the PK profile of CB-839 demonstrated a modest positive food effect and delayed absorption, which resulted in similar Cmax and Cmin for the 600 mg TID and 600 mg BID fed regimens. Given the favorable adverse event profile observed with the 600 mg BID fed regimen, this is the favored dosing regimen.

Pharmacodynamics of CB-839 was also assessed in both studies. Glutaminase activity was measured in circulating platelets as well as tumor biopsy specimens. Blood samples collected at baseline and four hours following CB-839 treatment were assessed for glutaminase inhibition and demonstrated a dose dependent relationship. At a CB-839 treatment dose of 600 mg BID, greater than 90% glutaminase inhibition should be observed even at Cmin for most patients. An evaluation of glutaminase activity assessed approximately 4 hours after the C1D15 CB-839 dose within five (5) tumor specimens also demonstrated clear inhibition of glutaminase activity and suggested a dose-response relationship (18).

Based on both pharmacokinetics and pharmacodynamics, CB-839 600 mg BID or 800 mg BID for a 21-day treatment cycle, to be repeated every 21 days has been determined as the single agent dose for pursuit in further clinical trials.

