#### 10.1.6 Methods

Glutaminase activity level will be measured using a glutaminase inhibition assay in both solid tumors and platelets.

Tumor Biopsy Specimens: The glutaminase inhibition assay will be conducted during the phase II portion of the study and will require fresh frozen biopsy specimens. These will be obtained as described in section 10.1.3. Patients will undergo a pretreatment biopsy up to 14 days prior to the initiation of treatment, then will undergo a second biopsy on day 10-15 of treatment. *Only the post-treatment tumor biopsy will be used for the glutaminase activity assay.* Samples will be frozen in liquid nitrogen and transferred to the Translational Research and Pharmacology Core on dry ice. Specimens will be evaluated for glutaminase activity per the Glutaminase Activity Assay Protocol for Platelets and Tumor Biopsy Samples (methods provided in laboratory manual).

Platelets: The glutaminase inhibition assay will be conducted during the phase II portion of the study. 24ml of blood will be collected from each patient on day 10-15 of treatment and will be collected on the same day as the post-treatment tissue biopsy. Specimens will be evaluated for glutaminase activity per the Glutaminase Activity Assay Protocol for Platelets and Tumor Biopsy Samples (methods provided in laboratory manual). Processing of samples will be done for each of the sites as outlined in section 10.2.4 and per the laboratory manual.

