## 11.4 Calendar—Phase II Component

Study Days	Pre-Study a	Pre-treatment	CB-839 and cape, C1D1 b	CB-839 and cape, C1D8	CB-839 and cape, C1D15	Cycle 2 and beyond, Day 1	Cycle 3, Day 14-21	Every 9 weeks	30 Day Follow-Up
REQUIRED ASSESSMENTS									
Informed Consent	X								
Demographics	X								
Medical History	X								
Height	X								
Weight	X		X			X			X
Vitals	X		X			X			X
Physical Examination	X		X			X			X
Concomitant Med Assessment	X		X			X			
ECOG PS	X		X			X			X
Symptom/Adverse Event Assessment	X		X	X	X	X			X
CBC with diff d	X		X	X	X	X			X
Serum comprehensive panel d	X		X	X	X	X			X
CEA (carcinoembryonic antigen) blood test	X					X			
Pregnancy test (if applicable)	X								
DISEASE ASSESSMENT									
Tumor measurements		Tumor assessments are performed at baseline and every 9 weeks. Documentation (radiologic) must be provided for patient removed from study for progressive disease.							
CT chest, abdomen and pelvis	X						X	X g	
MISC ITEMS									
Tumor biopsy		X c			X e				
TREATMENT									
CB-839			X h			X			
Capecitabine			X h			X			
CORRELATIVE STUDIES									
Pharmacodynamic studies		X c			X c				
Pharmacokinetics (CB-839)					X f				

a All evaluations must be completed  $\leq$  21 days prior to administration of protocol therapy.

b Cycle 1, Day 1 assessments do not need to be repeated if done within 7 days of initiation of treatment.

c Tumor biopsy may be done up to 14 days prior to initiation of treatment. Please allow 28 days washout from prior systemic therapy prior to pre-treatment biopsy. Platelet glutaminase assay should be drawn the same day as performance of the tissue biopsy. Glutaminase activity will only be assessed on the post-treatment blood and tissue specimens.

d CBC with differential and comprehensive panel for day 1 of the treatment cycle may be drawn up to 24 hours prior to treatment. Serum comprehensive panel should include sodium, potassium, chloride, bicarbonate, BUN, creatinine, glucose, AST, ALT, alk phos, total protein, albumin, total bilirubin, direct bilirubin, magnesium and phosphorus.

e Post-treatment tissue biopsy may be performed day 10-15. Platelet glutaminase assay should be drawn the same day as performance of the tissue biopsy.

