f Pharmacokinetic sample should be drawn just prior to the administration of the morning dose of CB-839 and capecitabine.

g Restaging CT scans may be performed +/- 7 days at all timepoints beyond the cycle 3 evaluation.

h Treatment starts this day. CB-839 is to be taken twice daily continuously (21/21 days) and capecitabine is to be taken twice daily for 14/21 days).

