#### **14.4 Analytic Plan for Correlative Objectives**

All correlative studies will be performed in biospecimens from the intent to treat population of 18-40 patients from the phase II portion of the study. Pre- and post-treatment tumor samples from the same patients will be used for assessments, except glutaminase activity, which will be performed on post-treatment samples only (tumor samples and platelet samples). All correlative continuous measurements will be summarized using mean +/- SEM, range and median; all categorical measurements will be summarized using frequencies and proportions. Change in these measurements in tumors before and after therapy will be assessed using paired Wilcoxon tests. Unpaired Wilcoxon tests will be used for assessment of glutaminase activity in post-treatment samples only. Assuming a maximum of 40 patients (2-sided test with 0.05 significance level and 80% power), for the paired T-test we can detect normalized differences of 4.5 to 18.2% for standard deviations of the difference between pairs ranging from 0.10 to 0.40. Correlations of plasma trough levels and platelet glutaminase activity will be calculated using Spearman correlation coefficients. Assuming a maximum of 40 patients, 2-sided test with 0.05 significance level, we have >98% power to detect a Spearman correlation coefficient of 0.60 or higher.

Whole exome sequencing and RNA sequencing will be performed on pre and post treatment tissue samples and compared for differences for all patients (n=40 patients maximum). All of these analyses are exploratory, hence no power calculations are shown.

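### The phase II CB-839 trough is fixed to day 15 while the glutaminase samples it is correlated with may be taken on any of days 10-15: a minor gap in a correlative analysis that is cheap to close

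*Combined protocol and SAP*

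**What the plan says.** **Trough.** In section 11.2.2 (Cycle 1, Day 10-15) the entry reads "Pharmacokinetic assessment prior to morning dose of CB-839 (day 15 only"). A footnote to the phase II calendar (11.4) adds: "Pharmacokinetic sample should be drawn just prior to the administration of the morning dose of CB-839 and capecitabine". The calendar marks PK only in the C1D15 column.

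**Glutaminase samples.** The calendar states: "Post-treatment tissue biopsy may be performed day 10-15". The platelet sample follows the biopsy, not the PK draw: "Platelet glutaminase assay (to be obtained the same day as the tumor biopsy"). Section 10.1.6 gives the same window: "24ml of blood will be collected from each patient on day 10-15 of treatment". None of these places states a time relative to the CB-839 dose. Section 10.3.3 (Collection of Specimens) requires the exact collection time in source documents and eCRFs, but for the PK sample only.

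**Analysis.** Section 14.4: "Correlations of plasma trough levels and platelet glutaminase activity will be calculated using Spearman correlation coefficients". It claims more than 98% power for a correlation of 0.60 with a maximum of 40 patients and a two-sided 0.05 test. Section 14.1.3 extends the trough correlation to biomarkers in tumours as well as platelets.

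**Whether PK is assayed.** The Protocol Summary says: "Day 15 blood samples will also be archived for as needed assessment of CB-839 pharmacokinetics". Section 10.2.6 says that all plasma samples will be analysed, and the phase II schema says that PK will be obtained and correlated with the other laboratory results.

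**The concern.** A correlation between exposure and target inhibition is most informative when both are measured at the same point in the dosing history. Here the two samples have separate schedules, and nothing in the protocol ties them together.

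Two things can separate them. First, dosing may change between the glutaminase day and day 15: sections 7.0 and 7.1.2 allow holds and interruptions, and section 6.2 says that missed doses are not replaced. Second, the glutaminase sample can fall anywhere in the dosing interval, whereas the trough is by definition at its end. CB-839 is described as a reversible inhibitor (1.2.1), and section 1.2.3 states: "The half-life of CB-839 was determined to be 4 hours". The earlier studies described in 1.2.3 sampled platelets at baseline and four hours after treatment, and tumour at about four hours after the C1D15 dose. This protocol's text carries no such control.

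Noise of this kind usually pulls a correlation toward zero. A weak observed correlation could then reflect the sampling rather than the biology. If collection times are not recorded, the analysis cannot adjust for this afterwards.

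The assay wording is a second, separate matter. If samples are assayed only when judged necessary, the 40 pairs assumed in 14.4 are not assured.

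**Working it through.** **1. The plan's own figure.** Inputs from 14.4: n = 40, correlation 0.60, two-sided alpha 0.05. Using the Fisher z approximation:

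power = Φ( atanh(ρ) / √(c/(n−3)) − 1.96 )

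Here c = 1 is the usual Pearson variance and c = 1.06 is Fieller's value for Spearman.

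- c = 1.06: 0.6931 / 0.1693 − 1.96 = 2.135, so power is 98.4%.
- c = 1: 0.6931 / 0.1644 − 1.96 = 2.256, so power is 98.8%.
- Simulation of the Spearman test (20,000 bivariate-normal samples): 98.4%.

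The more conservative Bonett-Wright variance, c = 1 + ρ²/2, gives 97.3%. The stated figure of more than 98% is reproduced.

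**2. How far apart the samples can be.** Day 15 − day 10 = 5 days at most. The gap is 0 days for a patient biopsied on day 15.

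**3. Does the day gap alone matter?** By day 10, 9 × 24 / 4 = 54 half-lives have passed since the first dose. With continuous, unchanged dosing the drug is at steady state, so troughs on days 10 and 15 should be similar.

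**4. Does time since dose matter?** By simple first-order decay over a 12-hour interval, concentration falls 2^(12/4) = 8-fold. This is a rough bound on concentration, not on inhibition. Section 1.2.3 reports delayed absorption with food, and it expects more than 90% inhibition even at the minimum concentration in most patients at 600 mg twice daily.

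**5. Size if mismatch adds noise.** The documents give no day-to-day or within-interval reliability, so the values below are assumptions. Attenuated ρ = 0.60 × √reliability, rounded to two decimals, with n = 40:

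| Assumed reliability | Attenuated ρ | Power, Fisher z (c = 1.06 to 1) | Power, simulated |
|---|---|---|---|
| 1.0 | 0.60 | 98.4-98.8% | 98.4% |
| 0.8 | 0.54 | 94.6-95.7% | 95.3% |
| 0.7 | 0.50 | 90.1-91.6% | 91.0% |
| 0.5 | 0.42 | 75.3-77.7% | 77.3% |

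**6. Size if fewer than 40 pairs are available.** Counts are assumed and ρ is kept at 0.60: n = 30 gives 93.8-95.0%; n = 20 gives 79.3-81.5%.

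**The case against.** The case for leaving the schedule alone has real weight.

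- **Steady state.** Day 10 is far beyond steady state, so under unchanged dosing a day 15 trough is a fair stand-in for a day 10 trough. This stands. It does not cover a hold or missed dose between the two days, although the documents give no frequency for these.
- **Near-complete inhibition.** A reader might infer from the 4-hour half-life that inhibition swings as widely as concentration. The documents do not support that. Section 1.2.3 expects more than 90% inhibition at the minimum concentration for most patients at 600 mg twice daily, and phase II uses 800 mg. Residual activity may still vary with time since dose, but by an unknown amount.
- **Mismatch is allowed, not required.** A reader might infer that every pair is unmatched. The calendar places biopsy, pharmacodynamic studies and PK in the same C1D15 column, and the footnote only permits earlier biopsy. Every pair is also within one patient.
- **Selective assay.** A reader might infer from the Protocol Summary that PK will be assayed only selectively. Section 10.2.6 and the schema say otherwise, so this is a conflict of wording rather than a settled plan.
- **Recording.** The CB-839 pill diary (Appendix II) captures dose times, so time since dose can be derived for the PK sample. The platelet and tumour assay follows a laboratory manual that is not among the documents and may specify timing. The gap is therefore shown for the protocol text only.
- **A common PK day.** Day 15 matches phase I and uses an existing laboratory visit. That is a genuine advantage of the current schedule.

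**Conclusion.** The point holds as a minor improvement to a correlative objective. The plan permits trough and glutaminase samples up to 5 days apart, and the protocol text neither fixes nor requires a record of when in the dosing interval the glutaminase samples are taken.

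The loss may be small. It depends on how often dosing changes between the two days and on how much residual glutaminase activity varies within a dosing interval, and the documents give neither. Over assumed reliabilities of 0.8 to 0.5, power at n = 40 would be about 95% down to 77%.

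A reader might infer that the stated power is wrong. It is not: it is correct for the inputs given, and what is uncertain is whether the sampling will deliver those inputs. Nor does 14.4 claim this power at the 18-patient minimum. The claim is tied to the maximum of 40.

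The conflict over the PK assay is a separate inconsistency. If the Protocol Summary wording governs, 40 pairs are not assured. The primary endpoint and the two-stage decision rule are unaffected by either matter.

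**What to change.** 1. In 11.2.2 and the 11.4 calendar, schedule the pre-dose PK sample for the day of the platelet and biopsy samples (day 10-15), using the same venipuncture as the platelet sample where possible.
2. Require the collection time and the time since last CB-839 dose to be recorded for the PK, platelet and biopsy samples.
3. Reconcile the Protocol Summary with 10.2.6 and the schema, so that PK is assayed in every phase II patient who has a platelet sample.

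The cost is wording in the calendar, protocol and laboratory manual, and assay of all stored PK samples. The roughly 2 mL PK draw is already planned, so no procedure is added. The downside is that the draw must be coordinated with the biopsy visit. For patients biopsied before day 15, the trial also gives up the PK day shared with phase I and the convenience of the existing day 15 laboratory visit.
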